For unvaccinated SOT recipients (Group A1 and Group A2), laboratory assessments for safety related to kidney function for kidney SOT recipients (serum creatinine, urine protein, and UPCR) and liver function for liver SOT recipients (alanine aminotransferase [ALT], aspartate aminotransferase [AST], alkaline phosphatase [ALP], and bilirubin) will be monitored on Day 1, Day 8, Day 29, Day 36, and Day 57 for SOT recipients who receive 2 doses only (Group A1) and on additional Days 85, 92, and Day 113 for SOT recipients who receive 3 doses (Group A2).

For previously vaccinated SOT recipients (Group A3), laboratory assessments for safety will be monitored on Day 1 (dose 3), Day 8, and Day 29.

After Day 57 (for unvaccinated SOT participants who receive 2 doses [Group A1]) or after Day 113 (for unvaccinated SOT participants who receive 3 doses [Group A2]), or after Day 29 (for previously vaccinated SOT recipients who receive dose 3 [Group A3]), the investigator will review standard-of-care laboratory assessments related to kidney and liver function and report any laboratory-related AEs and suspected or confirmed events of organ transplant rejection until the EOS.

Part B - Booster Phase

Part B is designed to offer participants in Part A, who are at least 4 months from the last dose, the option to request a BD (100 µg) of the prototype mRNA-1273 (Group B2, Group B3, and

Group B5). Part B is also designed to enroll SOT participants who completed primary vaccination series with mRNA or non-mRNA COVID-19 vaccine under the EUA who are at least 4 months from last dose (Table 3). At least 50 SOT recipients who completed primary vaccination series with a non-Moderna COVID-19 vaccine under the EUA (outside of the mRNA-1273-P304 study) will be enrolled in Part B. In case a variant of concern emerges and available data show a decreased immune response after vaccination with the prototype 100 µg BD, the Part B Booster Phase may test or replace the prototype 100 µg BD with a variant-specific mRNA-1273 vaccine (ie, Omicron-specific or mRNA-1273.529).

Table 3: Primary Series Vaccination for Booster Dose Eligibility

Primary Series Vaccine	Primary Series Number of Doses
mRNA COVID-19 vaccine (ie, Moderna, Pfizer)	3 doses
Non-mRNA COVID-19 vaccine (ie, Janssen)	2 doses or at least 1 dose combined with an mRNA COVID-19 vaccine

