7.1. Safety Assessments and Procedures

Safety assessments will include monitoring and recording of the following for each participant, according to the applicable SoE:

- Solicited local and systemic ARs ([Section 7.5.3](#)) that occur during the 7 days following each injection (ie, the day of injection and 6 subsequent days). Solicited

ARs will be recorded daily using the eDiary ([Section 7.1.1](#)). The definition of AR is presented in [Section 7.5.1](#).

- Unsolicited AEs observed or reported during the 28 days following each injection (ie, the day of injection and 27 subsequent days). Unsolicited AEs are defined in [Section 7.5.1](#).
- MAAEs throughout the study period.
- SAEs throughout the study period.
- AESIs throughout the study period.
- AEs leading to discontinuation from dosing and/or study participation (withdrawal) throughout the study period.
- Biopsy-proven organ rejection throughout the study period. A biopsy report will be needed for documentation.
- Safety laboratory assessments:

Part A

- For unvaccinated SOT recipients who receive the 2-dose regimen (Group A1), safety laboratory assessments related to kidney (for kidney transplant recipients) and liver function (for liver transplant recipients) will be monitored on Day 1, Day 8, Day 29, Day 36, and Day 57. After Day 57, the investigator will review standard-of-care laboratory assessments related to kidney and liver function (as related to the SOT) and report any laboratory-related AEs and suspected or confirmed events of organ transplant rejection until the EOS.
- For unvaccinated SOT recipients who receive the 3-dose regimen (Group A2), safety laboratory assessments related to kidney (for kidney transplant recipients) and liver function (for liver transplant recipients) will be monitored on Day 1, Day 8, Day 29, Day 36, Day 57, Day 85, Day 92, and Day 113. After Day 113, the investigator will review standard-of-care laboratory assessments related to kidney and liver function (as related to the SOT) and report any laboratory-related AEs and suspected or confirmed events of organ transplant rejection until the EOS.
- For previously vaccinated SOT recipients who receive dose 3 (Group A3), safety laboratory assessments related to kidney (for kidney transplant recipients) and liver function (for liver transplant recipients) will be monitored on Day 1, Day 8, and Day 29. After Day 29, the investigator will review standard-of-care

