8.3.2. Safety Analyses

Given that the study does not have a concurrent unvaccinated SOT control group, descriptive statistics will be used to present safety data, and no comparisons with the healthy adult participants will be made.

All safety analyses will be based on the Safety Set, except summaries of solicited ARs, which will be based on the Solicited Safety Set. All safety analyses will be summarized by cohort and subcohort arm.

Safety and reactogenicity will be assessed by clinical review of all relevant parameters including solicited ARs (local and systemic events), unsolicited AEs, MAAEs, SAEs, AESIs, AEs leading to discontinuation from dosing and/or study participation (withdrawal), biopsy-proven organ rejection, safety laboratory assessments, vital sign measurements, and physical examination findings.

The number and percentage of participants with any solicited local AR, with any solicited systemic AR, and with any solicited AR during the 7-day Follow-up Period after each dose will be summarized.

The number and percentage of participants with unsolicited AEs, SAEs, MAAEs, Grade 3 or higher ARs and AEs, AESIs, AEs leading to discontinuation from dosing and/or study participation (withdrawal), and adjudicated biopsy-proven organ rejection will be summarized. Unsolicited AEs will be presented by MedDRA preferred term and system organ class.

The number of events of solicited ARs, unsolicited AEs/SAEs, MAAEs, and adjudicated biopsy-proven organ rejection will be reported in summary tables.

Clinical laboratory data will be summarized by severity for each visit (per Toxicity Grading Scale for Healthy Adult and Adolescent Volunteers Enrolled in Preventative Vaccine Clinical Trials, [DHHS 2007](#)) and as the maximum over all postvaccination visits. Graphical presentations may include box plots and shift plots. Evaluation of clinically significant changes in safety laboratory measurements will be considered independent of the toxicity grading scale.

For all other safety parameters, descriptive summary statistics will be provided, and [Table 6](#) summarizes the analysis strategy for safety parameters. Further details will be described in the SAP.

Table 6: Analysis Strategy for Safety Parameters

Safety Endpoint	Number and Percentage of Participants, Number of Events
Any solicited AR (overall and by local, systemic)	X
Any unsolicited AE	X
Any SAE	X
Any AESI	X
Any unsolicited MAAE	X
Any adjudicated biopsy-proven organ rejection	X

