8. Vital signs are to be measured pre- and post-dose on days of injection (Day 1, Day 29, and Day 85). When applicable, vital signs should be measured before blood collection. Participants who are febrile (body temperature $\geq 38.0^{\circ}\text{C}/\geq 100.4^{\circ}\text{F}$) before injection on Day 1, Day 29, or Day 85 must have the visit rescheduled within the relevant visit window to receive the injection. Afebrile participants with minor illnesses can be enrolled at the discretion of the investigator.
9. The pregnancy test at Screening, Day 1, and before the second and third study injections will be a point-of-care urine test. At the discretion of the investigator, a pregnancy test either via blood or point-of-care urine test can be performed at any time.
10. Samples for safety laboratory assessments (serum creatinine, urine protein, and UPCR for kidney transplant recipients only; ALT, AST, ALP, and bilirubin for liver transplant recipients only) must be collected prior to dosing on Day 1, Day 29, and Day 85.
11. After Day 113, the investigator will review standard-of-care kidney and liver laboratory assessments and report any laboratory-related AEs and suspected or confirmed events of organ transplant rejection until the EOS.
12. Samples for immunogenicity (bAb against SARS-CoV-2 spike protein and neutralizing antibody against SARS-CoV-2) and assessment of SARS-CoV-2 bAb against the nonvaccine antigen (nucleocapsid protein) must be collected prior to dosing on Day 1, Day 29, and Day 85.
13. For assessment of cellular immune response, blood samples will be collected on Day 1 (prior to dosing), Day 36, and Day 92 from a subset of at least 50 unvaccinated SOT recipients (kidney or liver).
14. The NP swab sample will be collected prior to dosing and used to ascertain the presence of SARS-CoV-2 via RT-PCR.

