- Imputation rules for missing AE dates are provided in [Appendix C](#).
- For laboratory assessments, if the majority of results are indefinite, imputation of these values will be considered. If the laboratory results are reported as below the LLOQ (e.g., <0.1), the numeric values will be imputed by  $0.5 \times \text{LLOQ}$  in the summary. If the laboratory results are reported as greater than the ULOQ (e.g., >3000), the numeric values will be imputed by ULOQ in the summary.
- For immunogenicity assessments, imputation of missing results will be considered based on description in [Section 6.4](#).
- Other incomplete/missing data will not be imputed, unless specified otherwise.

**Participant groups** will be summarized according to the schema below.

- Transplant status:
  - SOT Kidney
  - SOT Liver
  - SOT Total
  - 2-Dose Healthy
- Dosing regimens:
  - Overall
  - Unvaccinated SOTs Who Received 2 Doses
  - Unvaccinated SOTs Who Received 3 Doses
  - Previously Vaccinated SOTs Who Received a Third Dose
  - Total SOTs Who Received 3 Doses
  - Primary Series All SOTs Who Received a Booster Dose
- Primary Series All SOTs Who Received a Booster Dose:
  - Overall
  - 3-Dose Moderna
  - 3-Dose Pfizer

Confidential

- Other

Unless otherwise mentioned, the results of the analyses will be summarized according to the participant groups above. Subjects under the same dosing regimen may be combined for analyses regardless of BD. Participants that received booster may be analyzed separately from participants that did not receive booster.

**Subgroup analyses** for safety and immunogenicity endpoints may be analyzed in select subgroups specified below as applicable:

- Age (18 to < 65,  $\geq$  65)
- Time of post-transplantation (< 2,  $\geq$  2 years)
- Baseline SARS-CoV-2 Status in each part (Positive, Negative) (for safety data)
- Sex (Male, Female)
- Race (White, Communities of color)
- Anti-metabolite immunosuppression (Yes, No)
- Combination of immunosuppressants (Mycophenolate, Tacrolimus, and Prednisone; Mycophenolate and Tacrolimus; Tacrolimus; and Other)
- Previous induction therapy (Basiliximab or other monoclonal antibody; Basiliximab or other monoclonal antibody with steroids; Thymoglobulin; Thymoglobulin with steroids; or steroids alone)

All analyses will be conducted using SAS Version 9.4 or higher.

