### **6.3.3. Clinical Laboratory Results**

Clinical laboratory samples will be collected at the Day 1 visit and at post-baseline visits through the Day 57 visit for participants receiving 2 doses of IP, or through Day 113 visit for participants receiving 3 doses of IP, or through Day 29 visit for SOT participants that are previously vaccinated with Moderna COVID-19 vaccines. For participants that continue to Part B of the study and receive BD, clinical laboratory samples will be collected at BD-Day 1, BD-Day 8, and BD-Day 29. Results will be summarized using descriptive statistics at each visit by participant group and will be presented in a data listing for the Safety Set.

Using the Toxicity Grading Scale for Healthy Adult and Adolescent Volunteers Enrolled in Preventative Vaccine Clinical Trials (DHHS 2007), as described in [Table 5](#), the number and percentage of participants experiencing clinical laboratory abnormalities and changes from baseline values at each visit will be summarized by severity grade and participant group. Similarly, clinical laboratory toxicity will be summarized as the maximum over all post-injection visits. Clinical laboratory results and their toxicity grades will also be listed for the Safety Set.

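### The worst laboratory grade and the change from baseline cover different spans in Groups A2 and A3, so the pooled 3-dose row mixes unlike quantities

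*SAP*

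**What the plan says.** SAP 6.3.3 (Clinical Laboratory Results) plans two toxicity summaries. The first is by visit: abnormalities and "changes from baseline values at each visit will be summarized by severity grade and participant group". The second is an overall worst grade: "Similarly, clinical laboratory toxicity will be summarized as the maximum over all post-injection visits". Protocol 8.3.2 has the same rule, "and as the maximum over all postvaccination visits". Neither text splits the maximum by dose.

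The draw schedules differ by group. For Group A2 (unvaccinated transplant recipients, three study doses), Protocol 7.1 says laboratory tests "will be monitored on Day 1, Day 8, Day 29, Day 36, Day 57, Day 85, Day 92, and Day 113". For Group A3 (two earlier Moderna doses, one study dose), Protocol 3.1 says "laboratory assessments for safety will be monitored on Day 1 (dose 3), Day 8, and Day 29". Footnote 10 to Protocol Table 8 says the A2 samples "must be collected prior to dosing on Day 1, Day 29, and Day 85".

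SAP 6.1 defines baseline as the last value before the first dose of study product. Its default reporting groups include "Total SOTs Who Received 3 Doses", which combines A2 and A3. SAP 6.1 also places A3 results at the visits tied to the third injection. SAP Appendix B does the same in the Safety Lab rows of Table 3 and in Table 4, although the text introducing Table 4 limits the alignment to certain summaries that it does not name.

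**The concern.** The percentage of participants whose worst grade reaches a given level can only grow as draws are added. A group observed seven times can therefore show a higher figure than a group observed twice, even when the risk at each draw is the same. In A2 the worst grade may also have been reached entirely before dose 3, yet it would be reported beside, and pooled with, an A3 figure that follows dose 3 alone.

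Aligning visits does not align the baseline. At the visit 28 days after dose 3, the A2 change carries the effect of three doses and the A3 change the effect of one.

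Change in liver and renal function is a Part A secondary endpoint, and safety of the 3-dose regimen is a primary objective. A pooled 3-dose row is the figure a reader is likely to quote. As planned, its worst-grade and change entries describe no single exposure.

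**Working it through.** **Scheduled Part A draws after the first study dose** (Protocol 3.1 and 7.1)

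| | A2 | A3 |
|---|---|---|
| Draw days | 8, 29, 36, 57, 85, 92, 113 | 8, 29 |
| Number of draws | 7 | 2 |
| Span | 113 − 1 = 112 days | 29 − 1 = 28 days |
| Study doses covered | 3 | 1 |
| Draws before dose 3 | 5 (Day 85 is pre-dose); 5/7 = 71% | 0 |
| Draws after dose 3 | 2 (Days 92 and 113) | 2 (Days 8 and 29) |

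These are scheduled counts. SAP 6.1 also lets unscheduled values into maxima.

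**Change from baseline at the aligned visits** (baseline from SAP 6.1, alignment from SAP Table 4)

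- 7 days after dose 3: A2 spans 92 − 1 = 91 days; A3 spans 8 − 1 = 7 days.
- 28 days after dose 3: A2 spans 113 − 1 = 112 days and three doses; A3 spans 29 − 1 = 28 days and one dose.

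**Size of the effect on the worst grade.** The plan gives no figure to reproduce and no risk per draw, so the risk p is an assumption, set equal in both groups. With k independent draws, P(at least one) = 1 − (1 − p)^k.

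| p per draw | A2, k = 7 | A3, k = 2 | Ratio |
|---|---|---|---|
| 1% | 6.8% | 2.0% | 3.4 |
| 5% | 30.2% | 9.8% | 3.1 |
| 10% | 52.2% | 19.0% | 2.7 |
| 20% | 79.0% | 36.0% | 2.2 |

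Draws from one person are correlated. A beta-binomial model with within-person correlation ρ, a = p(1 − ρ)/ρ and b = (1 − p)(1 − ρ)/ρ gives P(none in k) as the product of (b + i)/(a + b + i) for i = 0 to k − 1. At p = 5%:

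| ρ | A2 | A3 | Ratio |
|---|---|---|---|
| 0.3 | 16.9% | 8.3% | 2.0 |
| 0.6 | 10.5% | 6.9% | 1.5 |
| 0.9 | 6.2% | 5.5% | 1.1 |

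**Effect on the pooled row.** If a share w of the pooled group is A2, the pooled figure at p = 5% with independent draws is w × 30.2% + (1 − w) × 9.8%. At w = 0.5 that is 20.0%. It can lie anywhere from 9.8% to 30.2% according to enrolment mix alone.

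**After restriction to draws following dose 3.** A2 has Days 92 and 113 (92 − 85 = 7 and 113 − 85 = 28 days). A3 has Days 8 and 29 (7 and 28 days). Both have two draws over 28 days, so equal risk per draw and equal correlation give a ratio of 1.0.

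**The case against.** The strongest reply is that SAP 6.3.3 already plans toxicity grades at each visit, and the visit rules place A3 on the dose-3 visits. Grades at 7 and 28 days after dose 3 can then be read side by side, one draw each. Creatinine is graded on absolute values and the liver tests on multiples of the upper limit of normal, so these grades do not depend on the differing baselines. This stands. A reader might infer that third-dose kidney and liver safety is not on one scale, or that the effect of dose 3 cannot be read from the planned tables at all. The documents do not support that.

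It is also fair that the laboratory endpoint is defined over the whole regimen, and that the plan is for estimation without comparisons between groups. That justifies an all-visits maximum within each regimen. It does not justify the pooled row, which is itself a planned estimate and combines two regimens observed for different lengths.

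Thirdly, rejection is not detected from this table. Protocol 7.6.1 relies on individual thresholds relative to baseline, repeat testing and independent committee review. Adjudicated rejection has its own summaries, and all laboratory results are listed. This stands too, so the consequence is for reporting and not for participant monitoring.

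Finally, independent draws are implausible under absolute grading, because a stable raised creatinine is graded every time. That shrinks the gap, as the correlated results show. It also favours a shift from the pre-dose-3 value, which separates a persistent abnormality from a new one.

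**Conclusion.** The point holds for two measures: the all-visits worst grade, and change from baseline at the dose-3-aligned visits. Neither is comparable between A2 and A3, and the pooled 3-dose row averages unlike quantities on both. The by-visit toxicity grades are not affected.

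With no true difference, the A2-to-A3 ratio of worst-grade percentages runs from about 3.1 (independent draws) to about 1.1 (correlation 0.9) at an assumed 5% per draw. Both the 5% and the correlations are assumptions. A reader might infer that A2 will look more toxic than A3; the documents support only that it can. The gap disappears if draws are perfectly correlated, and the true correlation is unknown. The draw counts, spans and baseline mismatch come directly from the documents and need no assumption.

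The plan handles comparable data with more care elsewhere. Solicited reactions are analysed separately for each injection (SAP 6.3.2), and vital signs have shift tables with a pre-booster baseline in Part B (SAP 6.3.5). The change is worth making because it alters reported figures at little cost.

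**What to change.** In SAP 6.3.3, add a dose-3 laboratory summary for A2, A3 and the pooled 3-dose row, containing:

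- the worst grade over the draws 7 and 28 days after dose 3 (A2 Days 92 and 113; A3 Days 8 and 29);
- change and shift from the pre-dose-3 value (A2 Day 85 pre-dose; A3 Day 1).

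Keep the all-visits maximum and the change from first-dose baseline, but show them by regimen only and leave them out of the pooled 3-dose row.

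The cost is SAP wording and one extra table. Every sample needed is already scheduled, including the Day 85 pre-dose draw, so no new data are required.

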### **6.3.4. Pregnancy Tests**

A point-of-care urine pregnancy test will be performed at the Screening Visit and before each dose, including BD. In addition, at the discretion of the investigator, a pregnancy test

Confidential

either via blood or point-of-care urine test can be performed at any time. A listing of all pregnancy tests for participants with positive pregnancy tests will be provided.

### **6.3.5. Vital Sign Measurements**

Vital signs will be graded using the Toxicity Grading Scale for Healthy Adult and Adolescent Volunteers Enrolled in Preventative Vaccine Clinical Trials (DHHS 2007). This grading scale is displayed in [Table 6](#).

Vital sign measurements, including systolic and diastolic blood pressures, heart rate, respiratory rate, and body temperature, and baseline height, weight, and BMI will be presented in a data listing.

The abnormalities meeting the toxicity grading criteria (Grade 2 or higher) in any vital sign measurement will be listed separately. If a subject has a vital sign result with Grade 2 or higher abnormality at any post-injection visit, then all results of vital sign measurement for that subject will be presented in the listing. The abnormal values meeting the toxicity grading criteria will be flagged in the data listing.

Observed values and changes from baseline for all vital sign measurements will be summarized at each visit by participant group as defined in [Section 6.1](#). Shift from baseline in the toxicity grades at each visit (including post-dose assessment on day of injection) and shift from baseline in the toxicity grades to the worst post-baseline result will also be summarized by participant group. Change from baseline results and shift from baseline in toxicity grades will be based on pre-booster baseline (collected prior to BD on BD-Day 1) for participants in Part B.

### **6.4. Immunogenicity Analysis**

Immunogenicity samples will be collected at baseline and post-baseline visits, as described in the Schedule of Events in Appendix 1 of Protocol Amendment 4. The PP Immunogenicity Set (Part A/Part B) is the primary analysis population used in the immunogenicity analyses, unless otherwise specified. The mITT set (Part A/Part B) will be used for sensitivity analyses. Concomitant medications and/or vaccines received during the study as described in Section 5.5.3 in Protocol Amendment 4 and Protocol Clarification Memorandum 11 as well as antiretroviral treatments that impact neutralizing antibody responses may be used to determine subject's immunogenicity samples that are eligible for the immunogenicity analyses. Participants will be summarized according to participant group as defined in [Section 6.1](#).

Confidential

The GM levels will be calculated using the following formula:

$$10^{\left\{ \frac{\sum_{i=1}^n \log_{10}(t_i)}{n} \right\}}$$

where  $t_1, t_2, \dots, t_n$  are  $n$  observed immunogenicity levels.

The GMFR measures the changes in immunogenicity levels within subjects. The GMFR will be calculated using the following formula:

$$10^{\left\{ \frac{\sum_{i=1}^n \log_{10}\left(\frac{v_{ij}}{v_{ik}}\right)}{n} \right\}} = 10^{\left\{ \frac{\sum_{i=1}^n \log_{10}(v_{ij}) - \log_{10}(v_{ik})}{n} \right\}}$$

where, for  $n$  subjects,  $v_{ij}$  and  $v_{ik}$  are observed immunogenicity levels for subject  $i$  at time points  $j$  and  $k$ ,  $j \neq k$

